5.5 Pharmacokinetic and CSF Biomarker Assessments

Blood samples for PK and immunogenicity assessments will be collected in all subjects. Paired [REDACTED] blood samples for PK [REDACTED] will also be collected in patients who consent to having lumbar punctures performed. Table 5.5-1 lists the sampling schedule to be followed for routine PK and immunogenicity samples. Blood samples should be drawn from a site other than the infusion site (ie, contralateral arm) on days of the infusion. All samples collected predose should be taken just prior to nivolumab administration, and end-of-infusion (EOI) samples should be taken as close to EOI as possible (preferably 2 minutes prior to EOI) on the contralateral arm (ie, the arm not for the infusion). All on-treatment PK time points are intended to align with days on which nivolumab is administered. If it is known that a dose is going to be delayed, then the predose sample should be collected just prior to the delayed dose. However, if a predose sample is collected but the dose is subsequently delayed, an additional predose sample should not be collected. Table 5.5-2 lists the sampling schedule to be followed for paired [REDACTED] blood samples. For those patients who are on-study prior to Revised Protocol 04, sampling should begin with the cycle the patients are on, according to Table 5.5-2. Further details of blood collection, [REDACTED] collection, processing, labeling, handling, storage, and shipment of samples will be provided in the Procedure Manual.

Table 5.5-1: Pharmacokinetic & Immunogenicity Blood Sampling Schedule

[figure not shown]
Study Day C1 – C8: 2-week cycles C9 and beyond: 4-week cycles	Event	Time (Relative to Start of Infusion) Hour: Min	Nivolumab PK Blood Sample	Nivolumab Immunogenicity Sample
C1D1	predose ^a	00:00	X	X
C3D1	predose ^a	00:00	X	X
C7D1	predose ^a	00:00	X	X
C9D1	predose ^a	00:00	X	X
C9D1	EOI ^b	00:30	X	

[figure not shown]
Table 5.5-1: Pharmacokinetic & Immunogenicity Blood Sampling Schedule

Study Day C1 – C8: 2-week cycles C9 and beyond: 4-week cycles	Event	Time (Relative to Start of Infusion) Hour: Min	Nivolumab PK Blood Sample	Nivolumab Immunogenicity Sample
C10D1	predose ^a	00:00	X	
C13D1	predose ^a	00:00	X	X
C17D1	predose ^a	00:00	X	X
C21D1	predose ^a	00:00	X	X
D1 of every 6th cycle (24 weeks) after C21	predose ^a	00:00	X	X

^a All predose samples should be taken just prior to the start of nivolumab infusion (preferably within 30 minutes)

^b EOI samples should be taken as close to the end of infusion as possible (preferably two minutes prior to EOI) on the contralateral arm (ie, the arm not for the infusion). Study sites should ensure accurate collection of the time and date for PK and immunogenicity assessment are obtained.

5.7 Outcomes Research Assessments

Outcomes research data including health-related quality of life (QoL) and patient-reported symptom burden provide a more complete understanding of the impact of treatment by incorporating the patients' perspective. Treatment-related toxicities have been identified as a significant problem in both PCNSL, where neurotoxicity has been attributed to cognitive dysfunction, and in PTL, where patient age has reduced tolerance to aggressive chemotherapies. The importance of capturing patient-reported outcomes data has become critically important as

symptom management and maintaining QoL are key metrics for assessing overall treatment benefit.

5.7.1 EORTC QLQ-C30 and BN20

The EORTC QLQ-C30⁶⁸ is the most commonly used quality of life instrument in oncology trials. The instrument's 30 items are divided among 5 functional scales (physical, role, cognitive, emotional, and social), 9 symptom scales (fatigue, pain, nausea/vomiting, dyspnea, insomnia, appetite loss, constipation, diarrhea, and financial difficulties), and a global health/quality of life scale. With the exception of 2 items included in the global health/quality of life scale, for which responses range from 1 (Very poor) to 7 (Excellent), item responses range from 1 (Not at all) to 4 (Very much). Reduced cognitive function has been recognized as a significant problem in patients treated for PCNSL, and previous research has supported the validity of the cognitive functioning scale of the QLQ-C30 in a variety of populations. The EORTC QLQ-BN20⁶⁹ is a validated measure of concerns and symptoms specific to brain neoplasms. The questionnaire's 20 items are divided among multi-item scales measuring future uncertainty (4 items), visual disorders (3 items), motor dysfunction (3 items), and communication deficits (3 items), as well as single-item measures of problems with headaches, seizures, drowsiness, itchy skin, hair loss, lower extremity weakness, and bladder control. Each of the questionnaire's items uses a 4-point response scale ranging from 1 (Not at all) to 4 (Very much). Raw scores for the QLQ-C30 and QLQ-BN20 are transformed to a 0-100 metric such that higher values indicate better functioning or QoL or a higher level of symptoms. The QLQ-C30 will be administered to all treated subjects in both the PCNSL and PTL cohorts, while the QLQ-BN20 will be administered to all treated subjects in the PCNSL cohort, during the on-study and follow-up phases as outlined in [Section 5.1](#).

5.7.2 EQ-5D 3L

The EQ-5D-3L⁷⁰ is a generic multi-attribute health-state classification system by which health is described in 5 dimensions: mobility, self-care, usual activities, pain/discomfort, and anxiety/depression. Each dimension is evaluated using 3 levels: no problems, some problems, and severe problems. Responses to these 5 dimensions are converted into 1 of 243 unique EQ-5D health state descriptions, which range between no problems on all 5 dimensions (11111) to severe/extreme problems on all 5 dimensions (33333). Using appropriate country-specific value weighting algorithms, a respondent's self-described health state can be converted into a utility representing the societal desirability of his/her own health. In addition, the EQ-5D includes a visual analogue scale (VAS) allowing a respondent to rate his/her health on a scale ranging from 0–100 with 0 being the worst health state imaginable and 100 being the best health state imaginable. The EQ-5D-3L will be administered to all treated subjects in both the PCNSL and PTL cohorts during the on-study, follow-up, and survival follow-up phases as outlined in [Section 5.1](#).

5.8 Other Assessments

5.8.1 Immunogenicity Assessments

Serum samples collected at timepoints identified in [Section 5.1](#) will be analyzed by a validated immunogenicity assay. Additional characterization (ie, neutralizing antibodies) for any detected

anti-drug antibodies (ADA) response to nivolumab may also be performed using a validated functional cell-based assay. All on-treatment timepoints are intended to align with days on which study drug is administered, if dosing occurs on a different day, the immunogenicity sampling should be adjusted accordingly. Selected serum samples may be analyzed by an exploratory method that measures anti-nivolumab for technology exploration purposes; exploratory data will not be reported.

In addition, serum samples designated for PK or biomarker assessments may also be used for immunogenicity analysis if required (eg, insufficient volume for complete immunogenicity assessment or to follow up on suspected immunogenicity related AE).

6 ADVERSE EVENTS

An *Adverse Event (AE)* is defined as any new untoward medical occurrence or worsening of a preexisting medical condition in a clinical investigation subject administered study drug and that does not necessarily have a causal relationship with this treatment. An AE can therefore be any unfavorable and unintended sign (such as an abnormal laboratory finding), symptom, or disease temporally associated with the use of study drug, whether or not considered related to the study drug.

The causal relationship to study drug is determined by a physician and should be used to assess all AEs. The causal relationship can be 1 of the following:

Related: There is a reasonable causal relationship between study drug administration and the AE.

Not related: There is not a reasonable causal relationship between study drug administration and the AE.

The term "reasonable causal relationship" means there is evidence to suggest a causal relationship.

Adverse events can be spontaneously reported or elicited during open-ended questioning, examination, or evaluation of a subject. (In order to prevent reporting bias, subjects should not be questioned regarding the specific occurrence of one or more AEs.)

Immune-mediated adverse events (IMAEs) are AEs consistent with an immune-mediated mechanism or immune-mediated component for which non-inflammatory etiologies (eg, infection or tumor progression) have been ruled out. IMAEs can include events with an alternate etiology which were exacerbated by the induction of autoimmunity. Information supporting the assessment will be collected on the subject's CRF.

BMS will be reporting AEs to regulatory authorities and ethics committees according to local applicable laws including European Directive 2001/20/EC and FDA Code of Federal Regulations 21 CFR Parts 312 and 320.

6.1 Serious Adverse Events

A **Serious Adverse Event (SAE)** is any untoward medical occurrence that at any dose:

- Results in death
- Is life-threatening (defined as an event in which the subject was at risk of death at the time of the event; it does not refer to an event which hypothetically might have caused death if it were more severe)
- Requires inpatient hospitalization or causes prolongation of existing hospitalization (see **NOTE** below)
- Results in persistent or significant disability/incapacity
- Is a congenital anomaly/birth defect
- Is an important medical event (defined as a medical event[s] that may not be immediately life-threatening or result in death or hospitalization but, based upon appropriate medical and scientific judgment, may jeopardize the subject or may require intervention [eg, medical, surgical] to prevent one of the other serious outcomes listed in the definition above.) Examples of such events include, but are not limited to, intensive treatment in an emergency room or at home for allergic bronchospasm; blood dyscrasias or convulsions that do not result in hospitalization.) Potential drug-induced liver injury (DILI) is also considered an important medical event. (See [Section 6.6](#) for the definition of potential DILI.)
- Admission for administration of anticancer therapy in the absence of any other SAEs (see **NOTE** below)

Suspected transmission of an infectious agent (eg, pathogenic or nonpathogenic) via the study drug is an SAE.

Although pregnancy, overdose, cancer, and potential DILI are not always serious by regulatory definition, these events must be handled as SAEs. (See [Section 6.1.1](#) for reporting pregnancies.)

Any component of a study endpoint that is considered related to study therapy (eg, death is an endpoint, if death occurred due to anaphylaxis, anaphylaxis must be reported) should be reported as SAE (see Section 6.1.1 for reporting details).

NOTE:

The following hospitalizations are not considered SAEs in BMS clinical studies:

- A visit to the emergency room or other hospital department < 24 hours, that does not result in admission (unless considered an important medical or life-threatening event)
- Elective surgery, planned prior to signing consent
- Admissions as per protocol for a planned medical/surgical procedure
- Routine health assessment requiring admission for baseline/trending of health status (eg, routine colonoscopy)
- Medical/surgical admission other than to remedy ill health and planned prior to entry into the study. Appropriate documentation is required in these cases.

- Admission encountered for another life circumstance that carries no bearing on health status and requires no medical/surgical intervention (eg, lack of housing, economic inadequacy, caregiver respite, family circumstances, administrative reason)
- Admission for administration of anticancer therapy in the absence of any other SAEs (applies to oncology protocols)

6.1.1 *Serious Adverse Event Collection and Reporting*

Sections 5.6.1 and 5.6.2 in the Investigator Brochure⁶⁴ represent the Reference Safety Information to determine expectedness of SAEs for expedited reporting. Following the subject's written consent to participate in the study, all SAEs, whether related or not related to study drug, must be collected, including those thought to be associated with protocol-specified procedures. All SAEs must be collected that occur during the screening period and within 100 days of the last dose of nivolumab. For subjects assigned to treatment and never treated with study drug, SAEs should be collected for 30 days from the date of treatment assignment. If applicable, SAEs must be collected that relate to any later protocol-specified procedure (eg, a follow-up biopsy).

The investigator must report any SAE that occurs after these time periods and that is believed to be related to study drug or protocol-specified procedure.

An SAE report must be completed for any event where doubt exists regarding its seriousness.

If the investigator believes that an SAE is not related to study drug, but is potentially related to the conditions of the study (such as withdrawal of previous therapy or a complication of a study procedure), the relationship must be specified in the narrative section of the SAE Report Form.

SAEs, whether related or not related to study drug, and pregnancies must be reported to BMS (or designee) within 24 hours of awareness of the event. SAEs must be recorded on the SAE Report Form; pregnancies on a Pregnancy Surveillance Form (electronic or paper forms). The preferred method for SAE data reporting collection is through the eCRF. The paper SAE/pregnancy surveillance forms are only intended as a back-up option when the eCRF system is not functioning. In this case, the paper forms are to be transmitted via email or confirmed facsimile (fax) transmission to:

SAE Email Address: Refer to Contact Information list.

SAE Facsimile Number: Refer to Contact Information list.

For studies capturing SAEs through electronic data capture, electronic submission is the required method for reporting. In the event the electronic system is unavailable for transmission, paper forms must be used and submitted immediately. When paper forms are used, the original paper forms are to remain on site.

SAE Telephone Contact (required for SAE and pregnancy reporting): Refer to Contact Information list.

If only limited information is initially available, follow-up reports are required. (Note: Follow-up SAE reports must include the same investigator term[s] initially reported.)

If an ongoing SAE changes in its intensity or relationship to study drug or if new information becomes available, the SAE report must be updated and submitted within 24 hours to BMS (or designee) using the same procedure used for transmitting the initial SAE report.

All SAEs must be followed to resolution or stabilization.

A SUSAR (Suspected, Unexpected Serious Adverse Reaction) is a subset of SAEs and will be reported to the appropriate regulatory authorities and investigators following local and global guidelines and requirements.

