8.4.3 Safety Analyses

The safety analysis will be performed in all treated subjects. Descriptive statistics of safety will be presented using NCI CTCAE version 4.03 by treatment group. AEs, drug-related AEs, SAEs, and drug-related SAEs will be tabulated using worst grade per NCI CTCAE v.4.03 criteria by system organ class and preferred term. On-study lab parameters including hematology, chemistry, liver function, and renal function will be summarized using worst grade per NCI CTCAE v.4.03 criteria.

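### Protocol Section 6.1 lists the same treatment admission both as an SAE criterion and as not an SAE; the two lists must be reconciled

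*Protocol*

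**What the plan says.** Section 6.1 of the protocol says that an SAE "is any untoward medical occurrence that at any dose" meets one of a list of criteria. One criterion is hospitalization: "Requires inpatient hospitalization or causes prolongation of existing hospitalization (see NOTE below". The last is "Admission for administration of anticancer therapy in the absence of any other SAEs (see NOTE below".

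The NOTE to which both bullets point opens with "The following hospitalizations are not considered SAEs in BMS clinical studies". Its last item is "Admission for administration of anticancer therapy in the absence of any other SAEs (applies to oncology protocols".

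Section 6.1.1 sets the collection period: "All SAEs must be collected that occur during the screening period and within 100 days of the last dose of nivolumab". It requires SAEs to reach the sponsor within 24 hours of awareness, and it gives a rule for unclear cases: "An SAE report must be completed for any event where doubt exists regarding its seriousness".

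On analysis, Section 8.4.3 states that "AEs, drug-related AEs, SAEs, and drug-related SAEs will be tabulated using worst grade per NCI CTCAE v.4.03 criteria", in all treated subjects. The SAP does not settle the point. Its Section 7.6.2 on SAEs only refers to a Core Safety SAP, which is not among the documents.

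**The concern.** One event stands on both the inclusion and the exclusion list of the same definition. This is current operative text, and neither a redaction nor the amendment history explains it. Sites apply the definition themselves, and it drives both 24-hour reporting and the SAE tables.

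The situation can be foreseen. Protocol Section 3.6 provides for subjects who stop nivolumab to proceed to allogeneic transplant. SAP Section 7.5.2.4 plans to summarize subsequent chemotherapy and autologous and allogeneic transplant. Where such treatment involves an admission within 100 days of the last dose, the site must decide which list applies. If sites decide differently, the SAE percentage mixes toxicity with routine admissions, to a degree that varies by site. The study has a single arm, so no control group would show the same inflation.

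**Working it through.** The plan states no figure that depends on this definition, so there is none to reproduce for it. The one safety figure in protocol Section 8.1, 90% probability of seeing at least one AE of 5% incidence in 45 subjects, is correct (1 − 0.95^45 = 0.9006). It does not bear on the point.

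**Step 1: compare the two entries.**

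| | Criterion list | NOTE |
|---|---|---|
| What the list does | Makes an event an SAE | Says the hospitalization is not an SAE |
| Event | Admission to give anticancer therapy, no other SAE | The same admission, in the same words |
| Closing parenthesis | Points to the NOTE | Says that it applies to oncology protocols |

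The event is identical, this is an oncology protocol, and the classifications are opposite.

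**Step 2: ask whether the pointer resolves it.** The hospitalization criterion carries the same pointer. The NOTE removes some admissions from that criterion and leaves the rest, so it is a general rule with exceptions. For the anticancer-therapy criterion, the NOTE removes the whole of it. If the NOTE governs, the bullet can never make anything an SAE. If the bullet has any effect, it contradicts the NOTE.

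**Step 3: see which way doubt falls.** Section 6.1.1 requires a report where seriousness is doubtful. A site that finds the two lists in conflict has a textual reason to report. Any error is therefore likely to be over-reporting.

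**Step 4: weight of one subject.** The inputs are the planned cohort sizes in protocol Section 8.1: 45 PCNSL and 20 PTL. For a subject whose only SAE is such an admission, the change in the percentage with any SAE is 100 × 1/N:

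- PCNSL: 100 × 1/45 = 2.2 percentage points
- PTL: 100 × 1/20 = 5.0 percentage points

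How many such subjects there would be cannot be derived from the documents.

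**The case against.** The strongest answer is that the text, read as a whole, already gives one result. The bullet sends the reader to the NOTE, and the NOTE is unqualified. A planned admission for treatment is also hardly an untoward occurrence, so it fails the opening words of the definition. On this view the bullet is a stray line, and the rule on doubtful seriousness never applies because the NOTE has removed the doubt. Much of this stands: the NOTE is the likelier reading, and over-reporting would lose no safety signal. But the protocol still names the admission as a criterion, and a site that reports on that basis is following the text.

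A reader might infer more than the documents support:

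- **That a large share of the study would change SAE status.** One could assume that 30% to 70% of 65 subjects start another therapy within 100 days and that 25% to 50% of those are admitted for it. This gives 65 × 0.30 × 0.25 = 4.9 to 65 × 0.70 × 0.50 = 22.8 subjects. The documents support neither rate. The product also counts subjects who have another SAE and so stay in the numerator under either reading. SAP Section 6.1.2 counts on-treatment events within 30 or 100 days depending on the analysis, so fewer would be affected in 30-day tables.
- **That high-dose methotrexate admissions after progression would drive the effect.** The documents name it as prior therapy (protocol Section 3.3.1, SAP Section 7.3.4) and in a washout exception before enrollment (protocol Section 3.3.2). They do not name it as subsequent treatment.
- **That the published SAE tables would be wrong.** The Core Safety SAP, the Data Presentation Plan and the CRF completion guidelines are not available here. They may screen out such reports.

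**Conclusion.** The SAE definition in Section 6.1 contradicts itself and is wrong as written. The likely consequence is some over-reporting of routine treatment admissions, uneven across sites, in both expedited reporting and the SAE tables. Its total size cannot be determined from the documents. What can be stated is the weight of each affected subject: 2.2 points on the any-SAE percentage in PCNSL and 5.0 in PTL. This assumes the planned cohort sizes, no other SAE in that subject, and no downstream step that removes the report. It also rests on at least some sites acting on the bullet and on some subsequent treatment involving admission, neither of which the documents establish. The point is minor: safety analysis is descriptive, and the response, progression and survival analyses do not use the SAE definition.

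**What to change.** Put the admission on one list only. The NOTE's heading states the sponsor's policy for its studies, so the consistent change is to delete the last bullet of the SAE criteria in Section 6.1 and keep the item in the NOTE.

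Tell sites by administrative letter, of which Section 9.1.1 requires investigators to inform their ethics committees, or include the change in the next amendment with the approval that needs.

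Before the SAE tables are run, query reports whose only seriousness criterion is admission for anticancer therapy, and reclassify those confirmed to have no other basis.

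The cost is one deleted line, one site communication with its ethics-committee step, and a short data query. If any such reports exist, SAE counts will fall by that number and follow the same rule at every site.

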6.2 Nonserious Adverse Events

A *nonserious AE* is an AE not classified as serious.

6.2.1 Nonserious Adverse Event Collection and Reporting

The collection of nonserious AE information should begin at initiation of study drug. Nonserious AE information should also be collected from the start of a placebo lead-in period or other observational period intended to establish a baseline status for the subjects.

Nonserious AEs should be followed to resolution or stabilization, or reported as SAEs if they become serious (see [Section 6.1.1](#)). Follow-up is also required for nonserious AEs that cause interruption or discontinuation of study drug and for those present at the end of study treatment as appropriate. All identified nonserious AEs must be recorded and described on the nonserious AE page of the CRF (paper or electronic).

Completion of supplemental CRFs may be requested for AEs and/or laboratory abnormalities that are reported/identified during the course of the study.

All nonserious AEs (not only those deemed to be treatment-related) should be collected continuously during the treatment period and for a minimum of 100 days following discontinuation of study treatment.

Every AE must be assessed by the investigator with regard to whether it is considered immune-mediated. For events which are potentially immune-mediated, additional information will be collected on the subject's CRF.

